8.2 AGENT ORDERING AND AGENT ACCOUNTABILITY

- 8.2.1 NCI-supplied agents may be requested by the Principal Investigator (or their authorized designee) at each participating institution. Pharmaceutical Management Branch (PMB) policy requires that agent be shipped directly to the institution where the patient is to be treated. PMB does not permit the transfer of agents between institutions (unless prior approval from PMB is obtained). The CTEP-assigned protocol number must be used for ordering all CTEP-supplied investigational agents. The responsible investigator at each participating institution must be registered with CTEP, DCTD through an annual submission of FDA Form 1572 (Statement of Investigator), Curriculum Vitae, Supplemental Investigator Data Form (IDF), and Financial Disclosure Form (FDF). If there are several participating investigators at one institution, CTEP-supplied investigational agents for the study should be ordered under the name of one lead investigator at that institution.
- 8.2.2 Active CTEP-registered investigators and investigator-designated shipping designees and ordering designees can submit agent requests through the PMB Online Agent Order Processing (OAOP) application (<https://eapps-ctep.nci.nih.gov/OAOP/pages/login.jsp>). Access to OAOP requires the establishment of a CTEP Identity and Access Management (IAM) account (<https://eapps-ctep.nci.nih.gov/iam/>) and the maintenance of an “active” account status and a “current” password. For questions about drug orders, transfers, returns, or accountability, call [contact] Monday through Friday between 8:30 am and 4:30 pm (ET) or email [contact] anytime.
- 8.2.3 Agent Inventory Records – The investigator, or a responsible party designated by the investigator, must maintain a careful record of the inventory and disposition of all agents received from DCTD using the NCI Drug Accountability Record Form (DARF). (See

the NCI Investigator's Handbook for Procedures for Drug Accountability and Storage.)

9 BIOMARKER, CORRELATIVE, AND SPECIAL STUDIES

As soon as possible after the patient is scheduled please send an email notification to the [name] lab ([contact]), [name] ([contact]), and [name] ([contact]) that the sample is scheduled. After the sample is drawn please call the [name] lab at [contact] to communicate that the sample is ready. Keep the sample on the unit at room temperature and the sample will be picked up by the lab. Correlative studies will be performed on all patients who enroll in the protocol (including those with HIV infection).

9.1 SERUM VEGFR2, PLGF, IL-4, IL-12, HGF, B-FGF – GROUP 1 ONLY

- a. Collection of Specimen(s): one 10-cc redtop serum tube
- b. Handling of Specimens(s): keep at room temp. The sample will be picked up by the [name] lab.
- c. Shipping of Specimen(s): There is no shipping; these studies apply to NCI only.
- d. Methods; Isolate serum from redtop serum tube, freeze, thaw, run sandwich ELISA or an electrochemiluminescent multiplexed sandwich immunoassay (Meso-Scale Discovery).
- e. Site(s) Performing Correlative Study: [name] Lab, DTB, [name].

9.2 CIRCULATING TUMOR CELLS, CIRCULATING ENDOTHELIAL PROGENITORS, MATURE APOPTOTIC ENDOTHELIAL CELLS, REGULATORY T CELLS (TREGS)*, EXHAUSTED CD8 T CELLS*, MYELOID-DERIVED SUPPRESSOR CELLS (MDSCS)*, AND Th1/Th2 T CELL POPULATIONS*

- a. Collection of Specimen(s): four 10-ml lavender top tubes
- b. Handling of Specimens(s): Keep at room temp. The sample will be picked up by the [name] lab.
- c. Shipping of Specimen(s): There is no shipping; these studies apply to NCI only.
- d. Methods: Cell-based analyses will be performed by multiparametric flow cytometry.
- e. Site(s) Performing Correlative Study: [name] Lab, DTB, [name].

Note: Subsets marked with an asterisk (*) will be applicable to Group 2 only.

9.3 INTRA-TUMORAL IMMUNE INFILTRATE, WHERE TUMOR SAMPLES ARE AVAILABLE

- a. Collection of Specimen(s): Tissue will be placed in media provided by the lab. The [name] lab will go to the OR or IR to be present at the time of the procedure.
- b. Handling of Specimens(s): On ice. Tumor will be immediately dissociated into single viable cells and viably frozen until thawing for multiparameter flow cytometric analysis.
- c. Shipping of Specimen(s): No shipping.
- d. Methods: Thaw and stain for immune subsets including but not limited to CD8,

- CD4, CD56, CD68 and analyze by multiparameric flow cytometry.
- e. Site(s) Performing Correlative Study; [name] Lab, DTB, [name].

9.4 SAMPLE STORAGE, TRACKING AND DISPOSITION

Samples will be ordered in CRIS and tracked through a Clinical Trial Data Management system. Should a CRIS screen not be available, the CRIS downtime procedures will be followed. Samples will not be sent outside NIH without appropriate approvals and/or agreements, if required.

Any specimens that are remaining at the completion of the protocol will be stored in the conditions described below. The study will remain open so long as sample or data analysis continues. Samples from consenting subjects will be stored until they are no longer of scientific value or if a subject withdraws consent for their continued use, at which time they will be destroyed.

If the patient withdraws consent the participant's data will be excluded from future distributions, but data that have already been distributed for approved research use will not be able to be retrieved.

The PI will record any loss or unanticipated destruction of samples as a deviation. Reporting will be per the requirements of section 7.2.

10 DATA COLLECTION AND EVALUATION

10.1 DATA COLLECTION

The PI will be responsible for overseeing entry of data into C3D, an in-house password protected electronic system; and ensuring data accuracy, consistency and timeliness. The principal investigator, associate investigators/research nurses and/or a contracted data manager will assist with the data management efforts. All data obtained during the conduct of the protocol will be kept in secure network drives or in approved alternative sites that comply with NIH security standards. Primary and final analyzed data will have identifiers so that research data can be attributed to an individual human subject participant.

All adverse events, including clinically significant abnormal findings on laboratory evaluations, regardless of severity, will be followed until return to baseline or stabilization of event. Patients will be followed for adverse events for a minimum of 30 days after removal from study treatment or until off-study, whichever comes first.

An abnormal laboratory value will be recorded in the database as an AE **only** if the laboratory abnormality is characterized by any of the following:

- Results in discontinuation from the study
- Is associated with clinical signs or symptoms
- Requires treatment or any other therapeutic intervention
- Is associated with death or another serious adverse event, including hospitalization.

- Is judged by the Investigator to be of significant clinical impact
- If any abnormal laboratory result is considered clinically significant, the investigator will provide details about the action taken with respect to the test drug and about the patient's outcome.

End of study procedures: Data will be stored according to HHS, FDA regulations, and NIH Intramural Records Retention Schedule as applicable.

Loss or destruction of data: Should we become aware that a major breach in our plan to protect subject confidentiality and trial data has occurred, this will be reported expeditiously per requirements in section [7.3.2](#).

11 STUDY CALENDAR

Baseline evaluations are to be conducted within 1 week prior to start of protocol therapy. Scans and x-rays must be done ≤ 4 weeks prior to the start of therapy. In the event that the patient's condition is deteriorating, laboratory evaluations should be repeated within 48 hours prior to initiation of the next cycle of therapy.

Group 1	Pre-Study	Wk 1	Wk 2	Wk 3 ^l	Wk 4	Wk 5	Wk 6	Wk 7	Wk 8	Wk 9	Wk 10	Wk 11	Wk 12	Wk 13 ^m	Off- Treatment	Follow-up Evaluations ⁱ
Sunitinib		A	A	A	A			A	A	A	A					
Informed consent	X															
Demographics	X															
Medical history	X															
Concurrent meds	X	X-----X														
Physical exam	X	X		X				X							X	
Vital signs	X	X		X				X							X	
Blood Pressure ^h	X	X	X	X	X	X	X	X	X	X	X	X	X			
Height	X															
Weight	X	X		X				X							X	
Performance status	X	X		X				X							X	X
CBC w/diff, plts ^l	X	X		X				X							X	
Serum chemistry ^a	X	X		X				X							X	
Urinalysis	X															
PT/PTT	X															
EKG	X															
Echocardiogram/MUGA scan ^k	X	X														
Adverse event evaluation		X-----X												X		
Tumor measurements	X	Tumor measurements are repeated every 6 weeks for patients on treatment < 1 year; every 12 weeks for patients on treatment ≥ 1 year. Documentation (radiologic) must be provided for patients removed from study for progressive disease.												X		
Radiologic evaluation	X	Radiologic measurements should be performed every 6 weeks for patients on treatment < 1 year; every 12 weeks for patients on treatment ≥ 1 year.												X		

Group 1	Pre-Study	Wk 1	Wk 2	Wk 3 ^j	Wk 4	Wk 5	Wk 6	Wk 7	Wk 8	Wk 9	Wk 10	Wk 11	Wk 12	Wk 13 ^m	Off- Treatment	Follow-up Evaluations ⁱ
B-HCG	X ^b															
TSH and Free T4	X							X								
Circulating angiogenic proteins ^d	X							X						X		
CEP/CEC/CTC ^e	X							X						X		
Tumor molecular profiling ^f and intra-tumoral immune infiltrate ^g	X														X	
Follow-up Evaluations per Section 5.4																X

A: Sunitinib: Dose as assigned; administration schedule
 
a: Albumin, alkaline phosphatase, total bilirubin, bicarbonate, BUN, calcium, chloride, creatinine, glucose, LDH, phosphorus, potassium, total protein, SGOT [AST], SGPT [ALT], sodium; at baseline; on weeks 1 and 3 for Cycle 1; and then on Weeks 1 and 7 only for subsequent cycles, unless clinically indicated.
 
b: Serum pregnancy test (women of childbearing potential).
 
c: Off-study evaluation.
 
d: Serum VEGFR2, PlGF, IL-4, IL-12, HGF, b-FGF will be collected at baseline; on Week 7 (= Cycle 2, Week 1), and Week 13 (= Cycle 3, Week 1) at NCI only
 
e: Circulating endothelial cells, circulating endothelial progenitor cells, and circulating tumor cells will be collected at baseline; on Week 7 (= Cycle 2, Week 1), and Week 13 (= Cycle 3, Week 1) at NCI only
 
f: only in patients who also enroll in pilot study 11-C-0096
 
g: only in patients who donate fresh tissue
 
h: BP will be measured at baseline, and then weekly thereafter; i.e., at every clinic visit, and at home on weeks when there is no clinic visit. See Appendix F.
 
i: Follow-up evaluations will be conducted by clinic visits or phone interviews yearly until death, in accordance with Section 5.4. Patients removed from treatment for unacceptable adverse event(s) will be followed clinically until resolution or stabilization of the adverse event, and then via clinic visits or phone interviews yearly until death.
 
j: Cycle 1 only
 
k: Echo will be done at baseline, on Cycle 1 Week 1, and then every other cycle; i.e., Cycles 3, 5, 7, etc., according to Section 5.1.3
 
l: CBC w/diff, plts: at baseline; on weeks 1 and 3 for Cycle 1; and then on Weeks 1 and 7 only for subsequent cycles, unless clinically indicated.
 
m: Week 13 refers to Cycle 3 Week 1 only
																

Group 2	Pre-Study	Wk 1	Wk 2	Wk 3	Wk 4	Wk 5	Wk 6	Wk 7	Wk 8	Wk 9	Wk 10	Wk 11	Wk 12	Wk 13	Off- Treatment	Follow-up Evaluations ^h
Sunitinib		A	A		A	A		A	A		A	A				
Informed consent	X															
Demographics	X															
Medical history	X															
Concurrent meds	X	X-----X														
Physical exam	X	X			X			X							X	
Vital signs	X	X			X			X							X	
Blood Pressure ^g	X	X	X	X	X	X	X	X	X	X	X	X	X			
Height	X															
Weight	X	X			X			X			X				X	
Performance status	X	X			X			X			X				X	X
CBC w/diff, plts	X	X			X			X			X				X	
Serum chemistry ^a	X	X			X			X			X				X	
Urinalysis	X															
PT/PTT	X															
EKG	X															
Brain imaging (MRI or CT w/contrast)	X															
Echocardiogram/MUGA scan ⁱ	X	X						X								
Adverse event evaluation		X-----X													X	
Tumor measurements	X	Tumor measurements are repeated every 6 weeks for patients on treatment < 1 year; every 12 weeks for patients on treatment ≥ 1 year. Documentation (radiologic) must be provided for patients removed from study for progressive disease.													X	

Group 2	Pre-Study	Wk 1	Wk 2	Wk 3	Wk 4	Wk 5	Wk 6	Wk 7	Wk 8	Wk 9	Wk 10	Wk 11	Wk 12	Wk 13	Off- Treatment	Follow-up Evaluations ^h
Radiologic evaluation	X	Radiologic measurements should be performed every 6 weeks for patients on treatment < 1 year; every 12 weeks for patients on treatment ≥ 1 year.													X	
B-HCG	X ^b															
TSH and Free T4	X							X								
Immune subsets ^d	X	X			X			X						X		
CEP/CEC/CTC ^e	X	X			X			X						X		
intra-tumoral immune infiltrate ^f	X														X	
Follow-up Evaluations per Section 5.4																X
	
A: Sunitinib: Dose as assigned; administration schedule
 
a: Albumin, alkaline phosphatase, total bilirubin, bicarbonate, BUN, calcium, chloride, creatinine, glucose, LDH, phosphorus, potassium, total protein, SGOT [AST], SGPT [ALT], sodium; at baseline, and every 3 weeks, unless clinically indicated.
 
b: Serum pregnancy test (women of childbearing potential).
 
c: Off-study evaluation.
 
d: Samples for Tregs, MDSCs, Th1/Th2, and exhausted T cell analysis will be collected at baseline; on Week 4 and 7 (= Cycle 2, Week 1 and Cycle 3, Week 1), and Week 13 (= Cycle 5, Week 1) at NCI only
 
e: Circulating endothelial cells, circulating endothelial progenitor cells, and circulating tumor cells will be collected at baseline; on Week 7 (= Cycle 2, Week 1), and Week 13 (= Cycle 3, Week 1) at NCI only
 
f: only in patients who donate fresh tissue
 
g: BP will be measured at baseline, and then weekly thereafter; i.e., at every clinic visit, and at home on weeks when there is no clinic visit. See Appendix F.
 
h: Follow-up evaluations will be conducted by clinic visits or phone interviews yearly until death, in accordance with Section 5.4. Patients removed from treatment for unacceptable adverse event(s) will be followed clinically until resolution or stabilization of the adverse event, and then via clinic visits or phone interviews yearly until death.
 
i: Echo will be done at baseline, on Cycle 1 Week 1, and then every other cycle; i.e., Cycles 3, 5, 7, etc., according to Section 5.1.3 for patients on treatment < 1 year; then every 12 weeks for patients on treatment ≥ 1 year.
															

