Limited data is available on CEP/CEC in RCC patients treated with sunitinib. Available data thus far have yielded conflicting results with regard to baseline CEP/CEC numbers or change in these parameters and clinical outcome.^{134,135} To explore the effects of sunitinib on CECs and CEP cells in patients with thymic malignancies, these will be assayed on pre-dose peripheral blood samples on days 1 and 14 of cycle 1. Two lavender top tubes of whole blood will be collected for CEC/CEP analysis, which will be performed by multi-parameter flow cytometry, in the [name] laboratory, DTB, NCI. Cells will be analyzed for forward and side scatter, and a dump channel will be created to exclude cells expressing hematopoietic markers, such as CD45. Endothelial cells will be identified using co-expression markers, such as CD31, and CD146 for mature endothelial cells and CD133 for CEP cells. The cell populations will also be analyzed for viability using scatter profiles and a vital stain (e.g., Hoechst 33258). Multi-parameter flow analysis will be performed with a flow cytometer equipped with FlowJo software, using a minimum of 500,000 events per analysis.¹³⁶⁻¹³⁹

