5 TREATMENT PLAN

5.1 AGENT ADMINISTRATION

Sunitinib will be administered on an outpatient basis. Reported adverse events and potential risks are described in Section 7. Appropriate dose modifications are described in Section 6. No investigational or commercial agents or therapies other than sunitinib may be administered with

the intent to treat the patient's malignancy.

- 5.1.1 For Group 1, sunitinib will be administered orally at a dose of 50 mg daily for 4 consecutive weeks followed by 2 weeks of rest with no sunitinib, every 6 weeks (4/2 schedule). For Group 2, sunitinib will be administered orally at a dose of 50 mg daily for 2 consecutive weeks followed by 1 week of rest with no sunitinib, every 3 weeks (2/1 schedule). Patients should be instructed to store sunitinib at room temperature. Patients will take sunitinib once daily, with or without food, as desired. Patients should be advised to drink plenty of water or take rehydration fluids to avoid dehydration if diarrhea occurs.
- 5.1.2 Because hypertension is a known and potentially serious but rare adverse event associated with sunitinib maleate treatment, patients will have their blood pressure monitored and recorded at baseline and weekly during treatment including the weeks off the investigational drug either at the doctor's office or using any calibrated electronic device (such as those found at a local drug store or pharmacy). [Appendix D](#) and [Appendix F](#) detail the collection and recording of blood pressure related information.
- 5.1.3 Baseline assessment of cardiac function (ECHO/MUGA) is required for all patients. Routine monitoring for cardiac function (ECHO/MUGA) should be performed at baseline and then every other cycle of treatment in the following groups of patients: (1) those entering the trial with NYHA Class II cardiac dysfunction (see [Appendix B](#)), (2) those with a history of Class II heart failure who are asymptomatic on treatment, and (3) in those previously exposed to anthracyclines or thoracic irradiation if the heart was included in the radiotherapy port.

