17.4 ANALYSIS OF SECONDARY ENDPOINTS

We will follow all patients from the time that they are enrolled in the trial until the time of death. Demographic information such as age, gender and race will be tabulated. Durations of response, progression free survival, and overall survival will be determined actuarially using the Kaplan-Meier method. The results of this analysis may be compared in an informal manner to any similarly defined curves available from other published studies in comparable patients with the same disease. Correlative studies are exploratory, hence statistical power calculations will not be provided. Expression levels of various proteins from pre- and post-treatment samples will be compared using an appropriate nonparametric test and pre-post differences between responders and non-responders using a Wilcoxon rank sum test. These latter evaluations will be considered exploratory and the resulting p-values will be presented as being exploratory and without

adjustment for multiple comparisons.

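### Group 2 calendar footnote e carries Group 1's 6-week cycle labels, so the circulating-cell draw times conflict within the calendar and with section 2.4.3

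*Combined protocol and SAP*

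**What the plan says.** Section 5.1.1 sets the cycle lengths. Group 1 takes sunitinib for "4 consecutive weeks followed by 2 weeks of rest with no sunitinib, every 6 weeks (4/2 schedule"). Group 2 takes "50 mg daily for 2 consecutive weeks followed by 1 week of rest with no sunitinib, every 3 weeks (2/1 schedule").

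Section 11 times the circulating-cell samples (endothelial cells, endothelial progenitors and tumour cells) in a calendar for each group:

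- **Group 1, footnote e:** "circulating tumor cells will be collected at baseline; on Week 7 (= Cycle 2, Week 1), and Week 13 (= Cycle 3, Week 1) at NCI only". The Group 1 grid row marks Pre-Study, week 7 and week 13.
- **Group 2, footnote e:** the same words, including "on Week 7 (= Cycle 2, Week 1), and Week 13 (= Cycle 3, Week 1) at NCI only". The Group 2 grid row marks Pre-Study and weeks 1, 4, 7 and 13.
- **Group 2, footnote d (immune subsets):** baseline, then "on Week 4 and 7 (= Cycle 2, Week 1 and Cycle 3, Week 1), and Week 13 (= Cycle 5, Week 1) at NCI only". Its grid row has the same marks as the circulating-cell row.

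Section 2.4.3, headed as applying to both groups, gives another schedule for the endothelial and progenitor cells: "these will be assayed on pre-dose peripheral blood samples on days 1 and 14 of cycle 1". The introduction to section 2.4 gives the same two days. Section 9.2 describes the tubes and handling but no draw times. On analysis, section 17.4 says: "Correlative studies are exploratory, hence statistical power calculations will not be provided".

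**The concern.** Footnote e names each Group 2 draw twice, by week and by cycle, and the two names point to different dates. Someone ordering by cycle label would draw at weeks 4 and 7, and someone ordering by week number at weeks 7 and 13. The grid row marks weeks 4, 7 and 13, plus a week 1 mark that footnote e does not explain. The background section asks for day 14 of cycle 1, which appears on neither calendar for this test.

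At stake is whether a sample recorded as a given post-treatment draw has the same elapsed time in every patient. Section 17.1 gives these assays as part of the reason for the 15-patient cohort. In so small a group, a few samples taken or labelled at the wrong week could blur any change from baseline.

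**Working it through.** **Inputs**

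- Cycle length L: 6 weeks in Group 1 and 3 weeks in Group 2 (section 5.1.1).
- Draw times: section 11, both calendars, grid rows and footnotes; sections 2.4 and 2.4.3.

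**Formula.** First week of cycle c = (c − 1) × L + 1.

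**Step 1: reproduce the footnote with Group 1's cycle length (L = 6).**

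- Cycle 2 Week 1 = 1 × 6 + 1 = week 7
- Cycle 3 Week 1 = 2 × 6 + 1 = week 13

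Both equalities in footnote e hold, and Group 1's grid agrees with its footnote.

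**Step 2: repeat with Group 2's cycle length (L = 3).**

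- Cycle 2 Week 1 = 1 × 3 + 1 = week 4
- Cycle 3 Week 1 = 2 × 3 + 1 = week 7
- Cycle 5 Week 1 = 4 × 3 + 1 = week 13

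Both equalities in Group 2 footnote e fail. All three equalities in Group 2 footnote d hold, so the calendar's own text confirms the 3-week mapping.

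**Step 3: list the Group 2 draw sets.**

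| Source | Draws |
|---|---|
| Grid row | Pre-Study, weeks 1, 4, 7, 13 |
| Footnote e, by week number | baseline, weeks 7, 13 |
| Footnote e, by cycle label | baseline, weeks 4, 7 |
| Sections 2.4 and 2.4.3 (endothelial and progenitor cells only) | cycle 1, days 1 and 14 |

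The three calendar sets share only baseline and week 7. If the week 1 mark is itself the baseline draw, the grid becomes baseline, 4, 7, 13, and there are still three distinct sets. Week 7 is the first post-baseline draw under the week-number reading and the second under the cycle-label reading. The first footnoted draw can thus fall 3 weeks apart (7 − 4) and the second 6 weeks apart (13 − 7).

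**Step 4: check the fourth schedule.** Day 14 falls in week 2 (days 8 to 14). Neither calendar marks week 2 for this test.

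**Step 5: see what relabelling alone would do.** Correcting the cycle labels removes the cycle-label set. Footnote e would still omit week 4 and say nothing about week 1, so the footnote and grid would still disagree.

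**The case against.** The strongest reply is that little need go wrong in practice, and much of it stands.

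- The grid contains every time in the other two calendar sets, so staff who follow it miss no calendar draw.
- Section 9.2 describes one blood collection for these cells together with the Group 2 immune subsets, and footnote d times those subsets correctly at weeks 4, 7 and 13. Blood is therefore due at those weeks whatever footnote e says.
- The draws are at NCI only, handled by one laboratory, and footnote e gives the week before the cycle label.

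These facts lower the risk. They do not say which schedule governs, and they do not address day 14.

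Three stronger readings are tempting, and the documents do not support them:

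- **That samples will be drawn at non-matching weeks.** For the reasons above, the documents support only that they may be.
- **That the pre-post and responder comparisons in section 17.4 are compromised for Group 2.** Section 17.4 names protein expression levels, and the serum protein panel is Group 1 only (section 9.1). Applying those tests to cell counts is an inference; for Group 2, section 17.1 promises only exploratory analyses, with no named test or post-treatment time.
- **That a planned comparison with Group 1 is lost.** No between-group biomarker comparison is planned; section 17.1 mentions informal comparison with the original schedule for response and PFS. Weeks 7 and 13 also survive under the grid and under the footnote's week numbers. Only the cycle-label reading drops week 13.

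**Conclusion.** Group 2 footnote e is wrong as written. Its cycle labels are those of a 6-week cycle, and they contradict section 5.1.1 and footnote d. The Group 2 calendar supports three draw sets for one test, and sections 2.4 and 2.4.3 add a fourth for the endothelial and progenitor cells. Draws may therefore be taken or labelled at inconsistent weeks.

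The consequence is limited to exploratory analyses in up to 15 patients, for which no power is claimed. Response rate, PFS, OS, safety, sample size and error rates are unaffected. The correction is worth making because the calendar is the operative sampling schedule and the cost is very small.

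This rests on two assumptions: that the grid columns are read correctly from the extracted table (the identical immune-subset row, which matches footnote d at weeks 4, 7 and 13, supports this), and that cycles run without delay, so that cycle and calendar week correspond.

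**What to change.** 1. In Group 2 footnote e, change the labels to Week 7 (= Cycle 3, Week 1) and Week 13 (= Cycle 5, Week 1).
2. Add Week 4 (= Cycle 2, Week 1) to footnote e, so that it matches the grid, footnote d and the shared collection in section 9.2.
3. State whether the week 1 mark in the grid is the pre-dose baseline or a separate draw.
4. Reconcile the cycle 1 day 1 and day 14 schedule in sections 2.4 and 2.4.3 with both calendars, either by removing it or by marking it there.
5. Add a sentence to section 17.4 that any pre-post change in these cell counts will be analysed by actual weeks since first dose, not by cycle label. If samples have already been drawn, this still applies, provided the draw dates are recorded.

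The cost is one footnote, one clarifying note to the grid, the matching lines in sections 2.4 and 2.4.3, and one sentence in section 17.4. Items 1, 2, 3 and 5 need no extra patients and, because week 4 is already marked in the grid, no extra visits. Item 4 would add a week 2 draw only if the sponsor chose to keep day 14.
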